16.0 Statistical Considerations and Methodology

16.1 Overview: This protocol will assess the efficacy of ponatinib in FGFR aberrant advanced biliary cancers using a two-stage phase II study design.

16.11 Primary Endpoint: The primary endpoint of this trial is the clinical benefit rate, which includes confirmed tumor response (CR or PR) or SD for 4 or more cycle. A confirmed tumor response is defined to be either a CR or PR noted as the objective status on 2 consecutive evaluations at least 8 weeks apart. Clinical benefit rate will be evaluated using all cycles of treatment. All patients meeting the eligibility criteria who have signed a consent form, have begun treatment, and have not been deemed a major treatment violation during the first cycle of treatment will be evaluable for response.

16.2 Statistical Design

16.21 The largest clinical benefit where the proposed treatment regimen would be considered ineffective in this population is 5%, and the smallest clinical benefit rate that would warrant subsequent studies with the proposed regimen in this patient population is 20%. The following two-stage Simon Optimum design uses 10 or 27 patients to test the null hypothesis that the true clinical benefit rate in a given patient population is at most 5%.

The null clinical benefit rate of 5% is based on response rates observed for refractory solid tumors with single agents in an unselected/empiric setting (Horstmann, E. et al., 2005).

16.211 STAGE 1: Enter 10 patients into the study. If 0 successes (i.e., patients deemed as having clinical benefit) are observed in the first 10 evaluable patients, we will consider this regimen ineffective in this patient population and terminate this study. Otherwise, if the number of successes is at least 1, we will proceed to Stage 2.

16.212 STAGE 2: Enter an additional 17 patients into the study. If 2 or fewer successes are observed in the first 27 evaluable patients, we will consider this regimen ineffective in this patient population. If 3 or more successes are observed in the first 27 evaluable patients, we may recommend further testing of this regimen in subsequent studies in this population.

16.213 NOTE: Accrual will be suspended between stages to allow patients to become evaluable for the primary endpoint.

16.211 Over Accrual: If more than the target number of patients are accrued, the additional patients will not be used to evaluate the stopping rule or used in any decision making process. Analysis involving over accrued patients is discussed in Section 16.313.

16.22 Sample Size: The two-stage study design to be utilized is fully described in Section 16.21. A minimum of 10 and a maximum of 27 evaluable patients accrued onto this study unless undue adverse events are encountered. We anticipate accruing an additional 3 patients to account for ineligibility, cancellation, major treatment violation, or other reasons. Thus, **a maximum of 30 patients will be accrued onto this study** in order to have 27 evaluable patients available for the statistical design described in Section 16.21.

16.23 Accrual Time and Study Duration: The anticipated accrual rate is approximately 3 patients per month, based on physician estimate. Therefore, the accrual period for this phase II study is expected to be 16 months (including a 6-month suspension in accrual to perform the Stage 1 analysis). The final analysis can begin approximately 22 months after the trial begins, i.e., as soon as the last patient has been observed for 6 months.

16.24 Power and Significance Level: Assuming that the number of successes is binomially distributed, the significance level is <0.15 and the probability of declaring that this regimen warrants further studies (i.e., statistical power) under various clinical benefit rates can be tabulated as a function of the true clinical benefit rate as shown in the following table.

If the true clinical benefit rate is...	0.05	0.10	0.15	0.20	0.25
Then the probability of declaring that the regimen warrants further studies is...	0.12	0.43	0.70	0.85	0.93
And the probability of stopping at Stage 1 is...	0.60	0.35	0.20	0.11	0.06

16.25 Other Considerations: Adverse events, quality/duration of response, and patterns of treatment failure observed in this study, as well as scientific discoveries or changes in standard care will be taken into account in any decision to terminate the study.

16.3 Analysis Plan: The analysis for this trial will commence at planned time points (see Section 16.23) and at the time the patients have become evaluable for the primary endpoint. Such a decision will be made by the Statistician and Study Chair, in accordance with Mayo Clinic Cancer Center (MCCC) Standard Operating Procedures, availability of data for secondary endpoints (e.g., laboratory correlates), and the level of data maturity.

16.31 Primary Endpoint

- 16.311 Definition: The primary endpoint of this trial is the clinical benefit rate as defined in Section 16.11.
- 16.312 Estimation: The proportion of clinical benefit rate will be estimated by the number of patients with clinical benefit (confirmed CR, confirmed PR, or SD for 4 or more cycles) divided by the total number of evaluable patients. A confidence interval for the true clinical benefit rate will be calculated using the approach of Duffy and Santner
- 16.313 Over Accrual: If more than the target number of patients are accrued, the additional patients will not be used to evaluate the stopping rule or used in any decision making processes; however, they will be included in final point estimates and confidence intervals.

16.32 Definitions and Analyses of Secondary Endpoints

- 16.321 Progression-free survival time is defined as the time from registration to the earliest date of documentation of disease progression. If a patient dies without a documentation of disease progression the patient will be considered to have had disease progression at the time of their death. In the case of a patient starting treatment and then never returning for any evaluations, the patient will be censored for progression 1 day post-registration. The distribution of progression-free survival time will be estimated using the method of Kaplan-Meier (1958).
- 16.322 Survival time is defined as the time from registration to death due to any cause. The distribution of survival time will be estimated using the method of Kaplan-Meier (1958).
- 16.323 CA 19-9 response is defined to be a $\geq 50\%$ reduction from baseline. The CA 19-9 response rate will be estimated by the number of CA 19-9 responses divided by the total number of evaluable patients. A confidence interval will be calculated based on the binomial distribution.
- 16.324 Adverse Events: All eligible patients that have initiated treatment will be considered evaluable for assessing adverse event rate(s). The maximum grade for each type of adverse event will be recorded for each patient, and frequency tables will be reviewed to determine patterns. Additionally, the relationship of the adverse event(s) to the study treatment will be taken into consideration.

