2.2 Secondary

2.21 To estimate progression free survival, overall survival, and CA19-9 response rate of these patients

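### Section 16.321 gives two conflicting PFS rules for a treated patient who dies before any evaluation, and does not say which prevails

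*Combined protocol and SAP*

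**What the plan says.** Section 2.2 makes PFS a secondary goal: "To estimate progression free survival, overall survival, and CA19-9 response rate of these patients". Section 16.321 then defines it in consecutive sentences.

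- Origin and event: "Progression-free survival time is defined as the time from registration to the earliest date of documentation of disease progression".
- Death: "If a patient dies without a documentation of disease progression the patient will be considered to have had disease progression", dated at the death. No exception is given.
- No return: "In the case of a patient starting treatment and then never returning for any evaluations", "the patient will be censored for progression 1 day post-registration". No exception is given here either.

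The curve is estimated by Kaplan-Meier. Section 16.322 defines overall survival without any such clause: "Survival time is defined as the time from registration to death due to any cause".

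**The concern.** The death sentence and the no-return sentence are both unconditional, and their conditions overlap. A patient who takes the drug and dies before coming back has died without documented progression and has also never returned. The first sentence makes that patient an event on the date of death; the second censors the same patient one day after registration.

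Missing data cannot justify the censoring, because the death would be known. Section 10.52 requires expedited reporting of any death within 30 days of the last dose, and Section 10.613 requires it on the case report forms. Section 13.3 sends patients who leave treatment without progression to event monitoring, which under Section 18.1 has a death form and runs for up to 2 years after registration.

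The case is not far-fetched on the protocol's own safety text. Section 8.41 describes a death from hepatic failure within a week of starting the drug. Section 9.4 says fatal vascular occlusion can occur within 2 weeks. Those reports come from other experience with the drug and give no rate for this population.

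At stake is whether an early failure counts in the PFS curve. As the text stands, that choice could be made after the deaths are known, in a single-arm trial of at most 30 patients.

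**Working it through.** **1. The plan's own figures.** The documents state no PFS target, so there is no PFS figure to reproduce. The design table in Section 16.24 was checked as a baseline. The probability of stopping at Stage 1 is (1−p)^10. The probability of declaring the regimen worth further study is the sum over x ≥ 1 of P(x successes in 10) × P(at least 3−x in 17). At true rates 0.05, 0.10, 0.15, 0.20 and 0.25 this gives 0.1204, 0.4324, 0.6980, 0.8541 and 0.9322, with stopping probabilities 0.5987, 0.3487, 0.1969, 0.1074 and 0.0563. All match the table. None of them uses PFS.

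**2. One patient under each sentence.** Take a patient who is registered, treated, and dies before any evaluation.

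| Rule | Condition met? | Status | Date |
|---|---|---|---|
| 16.321, death sentence | Yes | Event | Date of death |
| 16.321, no-return sentence | Yes | Censored | Day 1 |
| 16.322, overall survival | Yes | Event | Date of death |

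**3. Effect on the curve.** Let N be the patients in the PFS analysis, k the number who die before any evaluation, and m(t) the number still progression-free at t. Assume no other early censoring and take t after all k have died.

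- Death sentence: S(t) = m(t)/N.
- No-return sentence: the k patients leave before the first event, which is the same as deleting them, so S(t) = m(t)/(N−k).
- Ratio of the second to the first: N/(N−k).

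No PFS analysis set is defined, so N is shown at 27 (evaluable target) and 30 (maximum accrual, Section 16.22). The values of k are assumptions.

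| k | N = 27 | N = 30 |
|---|---|---|
| 1 | 27/26 = 1.038 (3.8%) | 30/29 = 1.034 (3.4%) |
| 2 | 27/25 = 1.080 (8.0%) | 30/28 = 1.071 (7.1%) |
| 3 | 27/24 = 1.125 (12.5%) | 30/27 = 1.111 (11.1%) |

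**4. On the probability scale.** Further assumptions: N = 27, exponential PFS with a 3-month median in the other patients, early deaths at about 0.5 months.

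| k | 8-week PFS, death sentence | 8-week PFS, no-return sentence | Median in months, death / no-return |
|---|---|---|---|
| 1 | 17/27 = 0.630 | 17/26 = 0.654 | 2.84 / 2.84 |
| 2 | 16/27 = 0.593 | 16/25 = 0.640 | 2.67 / 3.00 |
| 3 | 16/27 = 0.593 | 16/24 = 0.667 | 2.49 / 2.82 |

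Over assumed medians of 2 to 4 months and k from 1 to 3, the median shifts by 0 to 0.44 months at N = 27 and by about 0.2 to 0.8 months at N = 30.

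**5. Consistency with overall survival.** Suppose 2 of 27 patients die before any evaluation and nothing else has happened by then. Under the no-return sentence PFS is 25/25 = 1.00, while overall survival is 25/27 = 0.93. Every death should end both, so PFS ought not to exceed overall survival.

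**6. How wide the overlap is.** This depends on what an evaluation is.

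- Any scheduled visit: the first return is Cycle 1 Day 8 (Section 4.0), so about one week.
- The visit that Section 7.2 requires at least every 28 days: about four weeks.
- Tumor evaluation only (Section 11.1): about eight weeks.

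Patients who return once and later progress or die are not touched by the no-return sentence.

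**The case against.** The strongest reply is that this is an ambiguity and not a biased analysis. The death sentence is as unconditional as the one after it. Censoring a patient who never returns reads naturally as a rule for loss to follow-up with an unknown outcome. On that reading the death counts and the bias is zero. This stands. A reader might infer that the plan removes its earliest failures and that its PFS curve will be too high. The documents do not support that, because nothing says the censoring sentence prevails. That it comes second and is more specific makes such a reading possible but does not make it a stated rule.

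The second reply concerns scope. A reader might count every death in the first eight weeks as affected. That holds only if evaluations means scans alone, or if the patients also missed the earlier visits. Section 7.2 uses the word for the 28-day visit, and Section 10.6 grades adverse events at each evaluation, with such assessments scheduled from Day 8. Sections 3.15 and 3.19b also require ECOG 0 to 2 and a life expectancy of at least 3 months, so several deaths before any visit should not be presumed.

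The third reply is size. At k = 2 and N = 27 the 8-week difference is 0.640 − 0.593 = 0.047, about half of one standard error (√(0.593 × 0.407/27) = 0.095). With 8-weekly scans the Kaplan-Meier median falls mostly on scan dates (about 1.84, 3.68 and 5.52 months), so it may not move at all, and a quoted median shift would be a weak argument. This also stands. What remains is that any error goes in one direction only and is avoidable.

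**Conclusion.** Section 16.321 gives contradictory instructions for one narrow class of patient: treated, and dead before any evaluation. That is a conflict between two stated rules, not merely a missing detail. Its consequence is conditional. Under the death sentence there is no bias. Under the no-return sentence PFS is overstated by N/(N−k), which is 3.8% to 12.5% relative for 1 to 3 such deaths at N = 27, and it could exceed overall survival. These figures assume the number of early deaths, no other early censoring, and an analysis set of 27; the 8-week values and medians also assume the exponential shape and the 3-month median.

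Severity is low to moderate. PFS is descriptive, with no hypothesis or threshold. The two-stage rule in Section 16.21 uses clinical benefit alone. Section 16.11 does not exclude an eligible, treated patient from the evaluable set for dying early. Section 16.322 counts the death in full.

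**What to change.** Amend Section 16.321, before PFS is analysed, to state three things:

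- A treated patient who dies before any post-baseline evaluation has a PFS event on the date of death.
- Censoring at 1 day after registration applies only when neither a post-baseline evaluation nor a death is recorded.
- What counts as an evaluation for this rule: any scheduled visit, the 28-day visit, or a tumor evaluation.

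Report the number of patients censored at day 1 beside the PFS curve.

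The cost is one clause and one definition. No additional data are needed, since the deaths and their dates are already collected. The downside is that PFS may look slightly less favourable than it would under the censoring reading.

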4.0 Test Schedule

Cycle = 28 days

Tests and procedures	Active Monitoring Phase						
	≤14 days prior to registration	Cycle 1 Day 1 (± 2 days) prior to treatment	Cycle 1 Days 8, 15, 22 prior to treatment	Cycle 2 and beyond Day 1 (± 2 days) prior to treatment	Q 8 weeks from Cycle 1 Day 1 (± 5 days)	Every 3 Cycles starting at end of Cycle 3 (± 5 days)	End of treatment
History and exam, wt, ECOG	X			X			X
Height, Child Pugh score	X						
Vitals ³	X	X	X	X			X
Hematology group WBC, ANC, Hgb, PLT	X	X	X	X			X
Chemistry group Sodium, potassium, chloride, bicarbonate, total protein, albumin, calcium, glucose, BUN, total bilirubin, creatinine, alkaline phosphatase, SGOT (AST), SGPT (ALT)	X	X		X			X
Amylase ^R	X	X	X	X			
Lipase ^R	X	X	X	X			
CA19-9		X		X ⁵			
EKG ^R	X					X	
Echocardiogram	X			X ¹⁰			
Tumor measurement and Imaging (CT or MRI as clinically)	X ¹				X ²		

indicated)							
Pregnancy test	X ⁴						
Patient questionnaire booklet	X ⁹			X ⁹			
Adverse event assessment	X		X	X			
Research Archival Tissue (optional)	X ⁸						
Research Tissue Biopsy (optional)				X ^{7,R}			X ⁶
Research blood samples (Optional)	X			X			X

1. Imaging studies such as CT scans, and MRIs can be performed ≤ 28 days prior to registration. Use same imaging throughout the study. Assessment by physical exam should be done ≤ 14 days prior to registration.
 2. Tumor assessment must be performed at least every 8 weeks. Tumor assessment should be performed at any time during the treatment cycle that disease progression is clinically suspected so that patient can go off treatment and receive other therapy.
 3. Includes weight, blood pressure, pulse and temperature
 4. Women of childbearing potential only. Must be done ≤ 7 days prior to registration.
 5. Only to be collected if $> \text{ULN}$ on Cycle 1 Day 1
 6. If patient has experienced disease progression and at such time a standard of care biopsy is ordered by the treating physician, waste specimen will be collected, fresh frozen and stored for future correlative studies. Perform only if archival specimen was available.
 7. Perform only if archival specimen was available.
 8. Archival FFPE and/or fresh frozen tissue collected in setting of standard of care procedures.
 9. Patient questionnaire booklet must be used; copies are not acceptable for this submission. Booklet should be completed by patient prior to review of treatment response and discussions of patient's general health since last treatment evaluation.

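### Section 16.323 counts patients whose CA 19-9 is not elevated at baseline as marker non-responders, although the test schedule never re-measures them

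*Combined protocol and SAP*

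**What the plan says.** CA 19-9 response rate is a named secondary goal in 2.21: "To estimate progression free survival, overall survival, and CA19-9 response rate of these patients". Section 16.323 defines a response as a fall of at least 50% from baseline and then states: "The CA 19-9 response rate will be estimated by the number of CA 19-9 responses divided by the total number of evaluable patients". It adds: "A confidence interval will be calculated based on the binomial distribution". It gives no confidence level, no condition on the baseline value and no evaluable set specific to CA 19-9.

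The term evaluable comes from 16.11, where eligible, consented patients who have begun treatment and "have not been deemed a major treatment violation during the first cycle of treatment will be evaluable for response". CA 19-9 plays no part in that definition. Section 16.312 uses the same denominator phrase for clinical benefit: "SD for 4 or more cycles) divided by the total number of evaluable patients". For adverse events, 16.324 spells out a set of its own: all eligible patients who started treatment.

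The section 4.0 test schedule takes CA 19-9 on Cycle 1 Day 1 for every patient. Footnote 5 governs the later cycles. It begins "Only to be collected if" and sets the condition that the Cycle 1 Day 1 value was above ULN. The inclusion criteria in 3.1 require measurable disease (3.14) but say nothing about CA 19-9.

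**The concern.** The collection rule and the estimation rule do not fit together. A patient at or below ULN on Cycle 1 Day 1 can enroll and be evaluable under 16.11, yet has no scheduled post-baseline CA 19-9. Whatever the drug does, the protocol provides no value from which a 50% reduction could be shown. If the denominator is the 16.11 set, that patient counts as a marker failure.

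The published rate would then mix two things: how often the marker falls in patients who can be followed, and how many enrolled patients had a raised marker to begin with. Another cohort with the same drug effect but a different share of elevated patients would give a different rate. Section 16.5 commits the trial to reporting its secondary endpoints on ClinicalTrials.gov, so the figure will be read outside the study team. If the study team meant a marker-specific denominator, the plan does not say so, and two analysts could report materially different rates from identical data.

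**Working it through.** The plan states no expected CA 19-9 rate, precision or number elevated, so there is no CA 19-9 figure to reproduce. The nearest stated figures are the operating characteristics behind the 27 evaluable patients. An exact two-stage binomial calculation (10 patients, continue with at least 1 success; 27 in total, promising with at least 3) reproduces the table in 16.24. The probability of declaring the regimen promising is 0.120, 0.432, 0.698, 0.854 and 0.932 at true rates of 5%, 10%, 15%, 20% and 25%. The probability of stopping at Stage 1 is 0.599, 0.349, 0.197, 0.107 and 0.056. The sample size of 27 can therefore be taken as given.

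**Inputs from the documents:** 10 to 27 evaluable patients (16.22); the response definition, denominator and binomial interval (16.323); later sampling only if above ULN (4.0, footnote 5).

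**Assumptions, because the documents give no values:** share elevated at baseline f = 50%, 70% or 90%; response rate among followed patients p = 40%; 95% exact (Clopper-Pearson) intervals.

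**Expected rate as written.** Only elevated patients can supply responses, so the expected reported rate is f × p:

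- f = 0.5: 0.5 × 0.40 = 0.20
- f = 0.7: 0.7 × 0.40 = 0.28
- f = 0.9: 0.9 × 0.40 = 0.36

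**Example with 27 evaluable patients.** The number followed is m = 27f rounded, that is 14, 19 or 24. The number of responders x is 0.40m rounded, that is 6, 8 or 10.

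| Share elevated | As written, x/27 (95% CI) | Followed patients only, x/m (95% CI) | Highest rate possible as written, m/27 |
|---|---|---|---|
| 50% | 6/27 = 22% (9–42%) | 6/14 = 43% (18–71%) | 52% |
| 70% | 8/27 = 30% (14–50%) | 8/19 = 42% (20–67%) | 70% |
| 90% | 10/27 = 37% (19–58%) | 10/24 = 42% (22–63%) | 89% |

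**How far the two quantities differ in practice.** With x distributed Binomial(m, 0.40), the x/27 interval contains 40% with probability 0.51, 0.84 and 0.96 for the three shares. The x/m interval contains it with probability 0.97, 0.97 and 0.96. The lower figures do not mean that the x/27 interval is faulty. Against its own target (20%, 28% or 36%, with x distributed Binomial(27, 0.40f)) it covers about 97% of the time in all three cases. They show how often a reader who takes it as the response rate among followed patients would be misled.

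**If the trial stops at 10 patients** (5, 7 or 9 followed), the expected point estimate shrinks by the share followed. The interval is so wide that it still contains 40% with probability 0.92, 0.97 and 0.99.

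**A second set of assumptions** gives the same picture. With about 50% of followed patients responding and 20%, 30%, 40% or 50% not elevated, the written rule gives 11/27 = 41%, 10/27 = 37%, 8/27 = 30% and 7/27 = 26%. Among followed patients the rates are 11/22 = 50%, 10/19 = 53%, 8/16 = 50% and 7/14 = 50%.

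**The case against.** The strongest reply is that evaluable in this plan changes with the endpoint: 16.11 defines it for response, 16.213 and 16.3 speak of the primary endpoint, and 16.324 of adverse events. In a CA 19-9 paragraph it could mean evaluable for CA 19-9. That reading is possible, but no such set is defined anywhere, and 16.323 repeats the 16.312 wording. At best the denominator is open to choice once results are known.

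Second, the share of all evaluable patients with a 50% fall is a coherent, conservative quantity, and goal 2.21 refers to the enrolled patients as a whole. This stands as far as it goes: the binomial interval is valid for that share. But footnote 5 already treats non-elevated patients as uninformative for this marker, and counting them as failures contradicts that choice.

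Third, footnote 5 governs scheduled sampling only. An unscheduled local test could exist, so the accurate statement is that these patients have no scheduled post-baseline value.

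Fourth, the size is assumed throughout. It is small at 90% elevated and nil if every patient is elevated. The endpoint carries no test, threshold or stopping rule, and both rates could be computed from the data at analysis. All of this is right; it limits the weight of the point without removing it.

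**Conclusion.** The concern holds. Followed as written, 16.323 counts patients with no scheduled post-baseline CA 19-9 as non-responders and caps the rate at the share elevated at baseline. The rate is lowered whenever at least one evaluable patient is at or below ULN and at least one patient responds. The relative reduction equals the share not elevated: 50%, 30% or 10% under the main assumptions above. It matters most if many patients are not elevated and is minor if few are. The conclusion rests on reading evaluable in 16.323 as the 16.11 set, which is the natural reading and the only efficacy definition available. The decision rule in 16.21, the sample size and the power are untouched. The change should be made, but the trial's main conclusion does not depend on it.

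**What to change.** In 16.323, define the denominator as patients evaluable under 16.11 whose CA 19-9 is above ULN on Cycle 1 Day 1, and compute the binomial interval on that number. State how elevated patients without a post-baseline value are counted, for example as non-responders. Report alongside the rate how many evaluable patients were not elevated at baseline, so that a reader can recover the all-patient share.

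This takes two or three sentences and no new data, since the Cycle 1 Day 1 value is already scheduled for everyone. The price is a smaller denominator and a wider interval: in the 50% elevated example, 18–71% on 14 patients against 9–42% on 27. That width reflects the number of patients on whom the marker was actually followed.
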